Participants were able to use their workbooks to follow along with class content and guided physical activity sessions over the phone. Low-impact exercises were written out and transcribed for BHL facilitators so that they could be delivered verbally. Peer health navigation activities were also transitioned to a telephonic format and included extra guided physical activity sessions, identifying physical activity opportunities that could be conducted from home or safely in the community, meal planning, setting up grocery delivery at home, or applying for additional resources such as free ride cards and food stamps. By June 2020, peer health navigators were encouraged to meet with interested participants face-to-face under the appropriate COVID-19 safety protocols (i.e., everyone must wear face masks covering the nose and mouth, keep 6 feet of distance, and use hand sanitizer) to provide the intervention whenever possible. BHL and BHL+PHN participants continued to receive virtual punches on their cards and all gift card payments were mailed to their home addresses.

Statistical Analysis Plan

Due to missing data, data analysis plan was revised from 3x4 and 3x13 ANOVAs to 3x2 ANOVAs (treatment groups X timepoints [baseline & 8-month]) for all intent-to-treat analyses, minimizing missing data, retaining power, maintaining intended plans to observe interventions from pre-test to post-test. Post-hoc comparisons were conducted as needed. As-treated analyses were conducted through 2x2x2 ANOVAs (treatment groups [BHL & BHL+PHN] X timepoints [baseline & 8-month] X attendance [yes or no, attended at least once]). If significant findings were observed, secondary analyses incorporated 4-month (mid-test) and 12-month interviews (follow-up) to determine if any changes occurred during these timepoints.

Originally, it was also proposed that a few intervention-related variables may be included as potential covariates in the analyses. These variables included: Study site where interventions were hosted (i.e., HAH or Trilogy), method of participant compensation (i.e., raffle or punch card), and format of interventions (i.e., in-person or online). As the addition of these covariates would only allow for conservative analyses without meaningful interpretation, potential cohort effects were not examined. Still, demographics would have been included as covariates if any differences were observed across treatment groups at baseline.

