A power analysis was carried out prior to the beginning of the study in MPLUS using the Saris and Satorra (1993) method. Based on past research, an effect size (standardized weight change) of -.07 in the BHL condition and -.20 in the BHL+PHN condition was expected. A sample size of 210 has 81% power to detect group differences. Prior to conducting any analyses, the data was assessed for missing values, normality, and skewness/kurtosis.

Missing Data. If participants were missing data for some items within in a scale, these were imputed using the “mean of nearby points” method in SPSS. This method of imputation takes the average of up to two nearby points in the scale to calculate a value for missing data.

Drop-Outs. Drop-outs were defined as those participants who informed IIT research staff that they no longer wanted to participate in the intervention before the end of the 8-month period. Participants who dropped out of the BHL or BHL+PHN interventions were not omitted from the dataset unless they did not complete any survey assessments after the initial interview. In other words, if at least one additional survey assessment was completed following baseline, missing data was imputed as described above.

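### The 3x2 ANOVAs labelled intent-to-treat cannot include everyone randomised, and the imputation rule given for drop-outs yields no value for a wholly missed 8-month survey

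*Combined protocol and SAP*

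**What the plan says.** The Statistical Analysis Plan opens by explaining a change of method: "Due to missing data, data analysis plan was revised from 3x4 and 3x13 ANOVAs to 3x2 ANOVAs". The two timepoints are baseline and 8 months, and the reduced design is used "for all intent-to-treat analyses, minimizing missing data, retaining power". The 4- and 12-month surveys enter only secondary analyses, and only after a significant finding.

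The Missing Data paragraph gives one imputation method. Its trigger is "If participants were missing data for some items within in a scale", and it "takes the average of up to two nearby points in the scale to calculate a value for missing data".

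The Drop-Outs paragraph defines a drop-out as someone who told staff, before the end of the 8 months, that they no longer wanted the intervention. It continues: "Participants who dropped out of the BHL or BHL+PHN interventions were not omitted from the dataset unless they did not complete any survey assessments". The surveys meant here are those later than baseline. For the rest, "if at least one additional survey assessment was completed following baseline, missing data was imputed as described above".

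Under Study Procedures, all three arms have surveys at baseline, 4, 8 and 12 months, and monthly check-ins throughout the 12 months.

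**The concern.** Two statements in the plan do not hold when its own rules are followed.

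- **The label.** Intent-to-treat tells a reader that everyone randomised is analysed in the assigned arm. The plan instead removes some people because of what happened after randomisation, and the two-timepoint design removes others.
- **The cross-reference.** The plan implies that gaps left by drop-outs with any later survey were filled. The method it points to cannot fill a missed visit.

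The main arm contrast is at stake. If people without an 8-month value differ from those with one, and this loss is not the same across arms, the contrast among those observed is not the contrast among those randomised. Missing data were serious enough to change the analysis, yet the plan does not say how much was missing at month 8.

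**Working it through.** **1. Who can enter the 3x2 ANOVA under the written rules**

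| Participant | Rule in the plan | 8-month value |
|---|---|---|
| Has baseline and 8-month surveys, some items blank | Item imputation | Yes |
| BHL or BHL+PHN drop-out, no later survey | Omitted | No |
| BHL or BHL+PHN drop-out with only a 4- or 12-month survey | Retained, missing data imputed by the item method | None obtainable |
| Lost without telling staff, or IC-TAU without month 8 | No rule stated | None |

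**2. The item rule applied to a 12-item scale** (invented answers)

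- Third item missing, neighbours 3, 4 and 2, 5. Taking two points on each side gives (3+4+2+5)/4 = 3.5. Taking two points in all gives (4+2)/2 = 3. Either way there is a value.
- All 12 items missing. There are no nearby points in the scale, so there is nothing to average.

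The retained drop-out in row 3 therefore either leaves the main test or is filled by a method the text does not give. In the first case the 4- or 12-month data add nothing to the main result.

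**3. How large a bias could be**

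The only design figure nearby is 81% power at 210 participants. It cannot be reproduced because alpha, the correlation between visits and the model are not stated, and this point does not depend on it. The plan's expectation, "an effect size (standardized weight change) of -.07 in the BHL condition and -.20 in the BHL+PHN condition was expected", is used below only as a scale.

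Let p1 and p0 be the fractions missing month 8 in BHL+PHN and control. Let D1 and D0 be the mean change of the missing minus that of the observed in each arm. Then

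all-randomised contrast = observed contrast + p1·D1 − p0·D0.

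All rates and gaps here are assumptions, with an observed contrast of −0.20 and, except in the last row, D1 = D0 = D:

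| p1 | p0 | D = +0.20 | D = −0.20 |
|---|---|---|---|
| 0.25 | 0.25 | −0.20 | −0.20 |
| 0.25 | 0.10 | −0.20 + 0.15×0.20 = −0.17 | −0.23 |
| 0.25 | 0 | −0.15 | −0.25 |
| 0.25 | 0.25, with D0 = 0 | −0.15 | −0.25 |

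The last row shows that equal rates alone are not enough: the mechanism must match too. The row with no control losses is an extreme, not a forecast.

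**4. Simulation**

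Settings: two arms of 70; visits at baseline, 4 and 8 months; SD 1; equal correlation of 0.5, 0.7 or 0.9; true 8-month contrast −0.20 with linear change; log-odds of missing month 8 of +1 or −1 per unit of observed 4-month change; 5,000 replicates.

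| Missing at month 8 (active v control) | Absolute complete-case bias |
|---|---|
| 25% v 0% | 0.02 to 0.11 |
| 25% v 10% | 0.01 to 0.07 |
| 25% v 25%, same slope | at most 0.007 |

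A likelihood estimate that uses the 4-month visit was within about 0.005 of the truth throughout. That result depends on everyone having a 4-month visit. For 25% v 0% with slope +1, at correlations 0.5/0.7/0.9, complete-case bias is about 0.11/0.07/0.03. Likelihood bias is about 0.03/0.01/0.01 if half of those missing month 8 also miss month 4, and about 0.04/0.03/0.02 if 80% do.

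**5. Baseline-only participants**

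Suppose 10% or 25% of the active arm have baseline only and do not change, while the rest change by −0.20 relative to control. The all-randomised contrast is 0.90×(−0.20) = −0.18 or 0.75×(−0.20) = −0.15. Complete-case and likelihood estimates both stay near −0.20, so neither corrects for this group.

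**The case against.** The best defence is a modest reading. The Drop-Outs paragraph speaks of people kept in the dataset, not of people entered in the main ANOVA. Going to two timepoints fits an analysis of people with both visits, with only stray items filled. On that reading the faults are a loose label and missing denominators. This is plausible, but the analysis is then available-case, and the sentence saying that retained drop-outs' missing data were imputed still has to be explained.

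Nearby points might mean neighbouring visits. The text ties them to items and to the scale, so that reading is unsupported. If visits were meant, it is a different method and must be stated.

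A reader might also infer that baseline-only people were removed from the active arms but kept in IC-TAU. The documents do not support that. Drop-out is defined as leaving the intervention, which explains why the rule names only BHL and BHL+PHN. A baseline-by-8-month ANOVA cannot use a baseline-only person in any arm. A one-sided loss is therefore not shown.

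Two further points stand. Retaining drop-outs who have surveys in their assigned arm is consistent with intent-to-treat. Nothing here shows a fault in item imputation for partly completed scales.

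**Conclusion.** The point holds as a mismatch between label, rule and analysis. The 3x2 ANOVAs do not include everyone randomised, and the stated imputation cannot supply a missed 8-month survey. From the text, a reader cannot tell whether the main test is available-case or uses an undisclosed fill-in.

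It would go too far to say that the results are biased, or biased in favour of the intervention. No missing rates are given, so size and direction are unknown. Bias is near zero if the rate and mechanism of missingness are the same in all arms. Otherwise it can go either way: 0.03 SD for 25% v 10% missing with a common 0.20 SD gap, and 0.01 to 0.07 SD in the matching simulation, against an expected effect of 0.20. All of these rest on assumed rates and mechanisms. It should be fixed because the main contrast cannot be reproduced from the plan and the remedy needs no new data.

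**What to change.** 1. State that item imputation applies only to partly completed scales and not to missed assessments.
2. Estimate the 8-month arm contrast with a likelihood-based repeated-measures model with categorical time and an unstructured (or otherwise stated) covariance. Use all observed assessments in the assigned arm, under one rule for all three arms: baseline, 4, 8 and 12 months for survey outcomes, and all available monthly check-ins for the Healthy Lifestyle Behaviors score. Because the ANOVAs have already been run, report them alongside and identify the model as a revision.
3. Report by arm the numbers randomised, missing month 8, and with baseline only. For the check-in score, someone with no later survey may still have phone check-ins, so count by outcome.
4. Add one not-at-random sensitivity analysis, for example delta-adjusted multiple imputation, that includes baseline-only participants, because the model in step 2 does not correct for them.

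If steps 2 and 4 are not done, relabel the 3x2 ANOVAs as available-case and state who was analysed.

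The cost is SAP wording and a modest re-analysis of data already collected. Intervals will be somewhat wider than with filled-in values. The main model assumes data are missing at random, and it reduces bias less when people who miss month 8 also miss month 4.
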